### 5.2 Visit Windows

The follow-up schedule and analysis windows are listed below.

- Discharge visit (discharge day)
- 30-Day Visit  $\pm$  7 Days [23, 37 days]
- 6-Month Follow-up ( $180 \pm 30$  days) [150, 210 days]
- 1 year Follow-up ( $365 \pm 45$  days) [320, 410 days]
- 2 years ( $730 \pm 45$  days) [685, 775 days]
- 3 years ( $1095 \pm 45$  days) [1050, 1140 days]

	Revision Date: April 1, 2019		Rev	3.0	For Use Only by Affiliates of Edwards Lifesciences	Page 14 of 18
	Title	Statistical Analysis Plan for FORMA EFS				

## 6. DATA AND ANALYSIS CONVENTIONS

### 6.1 General Conventions

- For continuous variables, summary statistics will include number of observations, mean, median, standard deviation, minimum, maximum, and 95% confidence intervals (based on normal distribution) per table shells. Nonparametric techniques may be used if the data does not meet the assumptions of parametric tests.
- For ordinal data, the count and percentage of patients will be presented.
- For categorical and qualitative variables, summary statistics will include number of observations, percentage, and 95% Clopper-Pearson confidence intervals per table shells. In general, the denominator for the percentage calculation will be based on total number of patients with evaluable data for a specified time point unless otherwise specified. Patients with missing data will be excluded from the denominator.
- Survival analysis techniques will be used to analyze the time-to-event variables. Summaries will include the number of patients at risk, number of events, number of patients with the event, and Kaplan-Meier estimates at given time points. Patients without events will be censored at their last known event-free time point. If this event-free time point occurs after the analysis time point, the days to event variable will be set equal to the analysis time point so that the patient will be included in the analysis. For patients who did not have an event or early withdrawal and have not yet completed the analysis visit, they will be censored at their last participation date. Standard errors will be calculated using Greenwood's formula and SAS defaults will be used for confidence bands and transformations on  $S(t)$  for the confidence limits. Kaplan-Meier event rate plots will be presented via the cumulative hazard rate plotted against the days from implantation.

- [REDACTED]

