8.10 PATIENT STUDY COMPLETION

Study patients complete and exit the study when no additional follow-up visits, procedures, or data collection are required. Patients will then continue to be followed by their primary health care provider as required.

A patient will also be exited from the study in the following instances:

- Patient signs informed consent form, is deemed eligible but does not undergo the study procedure
- Patient has study procedure attempted (at least skin incision to introduce the FORMA System) and does not have the investigational device implanted (will exit study at the 1 month follow up visit)
- If the study device is explanted, the patient will be followed for 30 days after the explant procedure for safety evaluations only, and will be exited from the study at that point. If one or more ongoing adverse event(s) related to the explant procedure is unresolved 30 days after the explant, the patient will remain in the study until the adverse event(s) have been resolved, or 180 days post explant, whichever comes first
- Patient is lost-to-follow-up
- Patient withdraws participation from the study or is withdrawn from the study
- Patient expiration

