## 5. DEFINITIONS

### 5.1 Analysis Dates and Days

- Reference Start Date and Day 0

The reference start date is defined to be the date of the index procedure. The index procedure is defined as the time the first interventional access-related puncture (arterial) is established.

The reference start date is considered to be day 0.

- Last Participation Date

The Last Participation Date is defined as the last date the patient is seen (e.g. maximum of the last date of procedure date, discharge date, follow-up visit date, exit date, adverse event date, and laboratory test date).

- Last Participation Day

Last Participation Day = Last Participation Date – Reference Start Date

Note: Last Participation Day is used as censor day for Kaplan-Meier analysis.

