#### 8.4.2 Clinical parameters

Re-hospitalization rates will be assessed at 1 month, 6 months and annually up to 3 years.

Time to first Heart Failure Re-hospitalization will be assessed via the Kaplan-Meier method for the AT cohort. In addition, the HF Re-hospitalization rate (number of HF Re-hospitalization per patient-year) will be analyzed.

Patient specific functional status (NYHA Class), exercise capacity (6MWD), and quality of life (SF-12 and KCCQ) metrics will be assessed at baseline, 1 month, 6 months, and 1 year and beyond.

Patients that undergo any type of repair or replacement procedure for the tricuspid valve will be excluded from analysis at the time of the reintervention. Only data up to the point of reintervention will be used.

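### SAP 6.1 has the Kaplan-Meier event rate plots show the cumulative hazard, which read literally does not match the Kaplan-Meier estimates required in the same bullet

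*SAP*

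**What the plan says.** The time-to-event bullet in SAP 6.1 (General Conventions) lists what the summaries contain, including "number of patients with the event, and Kaplan-Meier estimates at given time points". It specifies Greenwood standard errors, with SAS defaults for the confidence bands and for the transformation of S(t) behind the limits. Its last sentence then sets the figure: "Kaplan-Meier event rate plots will be presented via the cumulative hazard rate plotted against the days from implantation". A redacted bullet follows.

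The one analysis that the readable text assigns to this method is in SAP 8.4.2: "Time to first Heart Failure Re-hospitalization will be assessed via the Kaplan-Meier method for the AT cohort". The same section has re-hospitalization assessed up to 3 years.

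On censoring, SAP 6.1 says "Patients without events will be censored at their last known event-free time point". SAP 5.1 adds "Last Participation Day is used as censor day for Kaplan-Meier analysis" and builds the underlying date as the "maximum of the last date of procedure date, discharge date, follow-up visit date, exit date, adverse event date, and laboratory test date". Protocol 8.10 lists "Patient expiration" among the ways a patient exits the study.

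**The concern.** The sentence on plots names one quantity, a Kaplan-Meier event rate, and prescribes another, the cumulative hazard. The Kaplan-Meier event probability is 1 - S(t) and lies between 0 and 1. The cumulative hazard is -ln S(t), is always at least as large, and has no upper bound. A programmer who follows the text would produce a figure whose curve sits above the table beside it, and whose axis can pass 1. The limits in the table are derived from S(t) and could not be drawn on that axis without being transformed.

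One objective of the study is to guide the design of later studies. A curve titled as an event rate is likely to be read as a probability and carried forward as a planning value.

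A lesser question concerns the same curve. Over 3 years some patients may die before any HF re-hospitalization. If those deaths are censored, 1 - KM estimates the risk with death set aside, not the proportion of patients re-hospitalized.

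**Working it through.** **1. Plot scale against table scale.** The documents state no event rate, so there is no planned figure to reproduce. The comparison is an identity: if the table shows p = 1 - S(t), the literal figure shows H = -ln(1 - p).

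| 1 - S(t) | -ln S(t) | Gap |
|---|---|---|
| 0.05 | 0.051 | 0.001 |
| 0.10 | 0.105 | 0.005 |
| 0.20 | 0.223 | 0.023 |
| 0.30 | 0.357 | 0.057 |
| 0.40 | 0.511 | 0.111 |
| 0.50 | 0.693 | 0.193 |

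The gap reaches 0.02 when 1 - S(t) is about 0.187. H passes 1 when 1 - S(t) exceeds 1 - exp(-1) = 0.632.

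Estimating the hazard by Nelson-Aalen instead changes little. Take n = 60 (the planned enrolment) with no censoring, and sum 1/(number at risk) over the events. Then 12 events give 0.221 against 0.200, 18 give 0.353 against 0.300, and 30 give 0.685 against 0.500.

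**2. What happens to a death before HF re-hospitalization.** Such a patient has not had the event, so the SAP 6.1 rule censors the patient. SAP 5.1 makes the last participation day the censor day and counts the exit date towards it. Protocol 8.10 makes death an exit. The readable rules therefore censor at or about death, without naming it.

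**3. Illustration of what that does to 1 - KM read as a proportion.** All rates here are assumptions; the documents give neither an HF re-hospitalization rate nor a death rate. With constant, independent hazards l (HF) and m (death):

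- 1 - KM at time T = 1 - exp(-lT)
- Cumulative incidence at T = l/(l + m) × (1 - exp(-(l + m)T))

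Worked case: assumed 3-year net risks of 40% for HF and 20% for death. Then 3l = -ln 0.6 = 0.511 and 3m = -ln 0.8 = 0.223. 1 - KM is 40.0%. The cumulative incidence is 0.511/0.734 × (1 - 0.480) = 36.2%. The excess is 3.8 points.

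| Assumed rates | Excess of 1 - KM at 3 years |
|---|---|
| No deaths | 0 |
| 3-year HF 20-70%, 3-year death 10% | 1.0 to 2.9 points |
| 3-year HF 20-70%, 3-year death 20% | 2.0 to 5.9 points |
| 3-year HF 20-70%, 3-year death 30% | 3.1 to 9.1 points |
| 1-year HF 20-30%, 1-year death 10-20% | 6.2 to 15.0 points |

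At 1 year the excess is at most 1.8 points under the 3-year assumptions, and 1.0 to 2.9 points under those in the last row. The ranges differ because the assumed rates differ.

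For scale, the exact 95% interval for 24 of 60 (40%) is 27.6% to 53.5%. For 12 of 30, the size of one subgroup in SAP 4, it is 22.7% to 59.4%. The as-treated cohort may be smaller than either.

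**The case against.** The strongest reply is that the phrase is a slip. In a bullet built on Kaplan-Meier estimates and S(t) limits, the writer probably meant the cumulative event rate. Even taken literally, -ln S(t) is a one-to-one transform of the same curve, so nothing is lost, and the correct probability is in the table. Much of this stands: no estimate is wrong and no test depends on the plot. It does not remove the need for the edit. SAP 1 presents the plan as detailed instructions and requires departures from it to be justified in the study report. Plotting the probable intent would depart from the written rule. If it is a slip, the text should say 1 - S(t).

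On deaths, the reply is that Kaplan-Meier with deaths censored is a legitimate cause-specific summary, that SAP 8.4.2 nowhere calls it a proportion, and that a redacted bullet follows the rule. All of that stands, which is why this part is only a suggestion.

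A reader might infer more in three ways:

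- **That the plan leaves the handling of death open.** It does not: the rules in SAP 5.1, SAP 6.1 and Protocol 8.10 together censor by default. Redacted text also cannot be counted as an omission.
- **That deaths would be hidden.** FDA Device Success (SAP 3.3.1) has being alive as a component at 1 month and at every later follow-up visit, and SAP 8.3 reports each component. SAP 7.1 tabulates disposition at each interval.
- **That the Kaplan-Meier results themselves are biased by a known amount.** The documents give no rates, so no amount can be derived.

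**Conclusion.** The plot instruction in SAP 6.1 should be corrected. As written it produces a figure on a different scale from the estimates and limits in its own bullet. The difference is about half a point at a 10% event rate, 2.3 points at 20% and 11.1 points at 40%. This follows from arithmetic and assumes only that the sentence is applied literally.

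The scope is small. It covers descriptive time-to-event figures, in practice the HF re-hospitalization curve. The tabulated Kaplan-Meier estimates, the 30-day safety and success endpoints (counts and percentages) and the HF rate per patient-year are unaffected.

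The point about deaths is secondary and optional. Its direction is certain if 1 - KM is read as the proportion re-hospitalized and any patient at risk dies. Its size rests wholly on assumed rates. In the worked case it is well inside the sampling uncertainty of a 60-patient study.

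**What to change.** **SAP 6.1.** Replace the reference to the cumulative hazard so that the sentence says the plots show 1 - S(t), with confidence limits on the same scale as the tabulated estimates. This changes one phrase and needs no new data.

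**SAP 8.4.2 (optional).** If the redacted bullet in SAP 6.1 already covers death, a cross-reference is enough. If not, keep the Kaplan-Meier analysis, state that it censors at death, and add the Aalen-Johansen cumulative incidence with death as a competing event as the estimate of the proportion re-hospitalized. This takes one or two sentences. The downside is one more descriptive estimate, which may differ little from 1 - KM if few patients die.

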### 6.2 Handling of Missing Data

All statistical analysis on the endpoints will be performed using only those patients with available data required for endpoint analysis. No missing value imputation will be performed.

 Edwards	Revision Date: April 1, 2019		Rev	3.0	For Use Only by Affiliates of Edwards Lifesciences	Page 15 of 18
	Title	Statistical Analysis Plan for FORMA EFS				

## **7. SUMMARY OF BASELINE INFORMATION**

### **7.1 Patient Enrollment and Accountability**

Patient enrollment for the ITT and AT groups will be summarized by each site and in total.

Disposition of patients at each follow up interval will be summarized in a table. If a patient discontinues prematurely from the study, the reason for discontinuation must be documented. The Study Exit case report form will be completed to document the reason for withdrawal.

### **7.2 Demographics and Baseline Characteristics**

Demographic and baseline characteristics, including but not limited to age, sex, and NYHA at baseline, will be summarized by counts and percentages for the ITT and AT populations.

### **7.3 Medical History and Prior Intervention**

Medical history and prior interventions will be summarized by counts and percentages. Cardiovascular Medical History and Risk Factors, Non-Cardiovascular Medical History and Risk Factors, and Prior Cardiovascular interventions or Surgeries will all be summarized.

### **7.4 Procedural Information**

Procedural information will be summarized including but not limited to procedure duration, duration of fluoroscopy time, volume of contrast used, and implantation status. In addition, the number of days spent in the ICU and total hospitalization for the index hospitalization will be summarized in a different table.

 Edwards	Revision Date: April 1, 2019		Rev	3.0	For Use Only by Affiliates of Edwards Lifesciences	Page 16 of 18
	Title	Statistical Analysis Plan for FORMA EFS				

## 8. ANALYSIS OF STUDY ENDPOINTS

### 8.1 Safety Endpoint

Safety will be analyzed as a composite endpoint of Major Adverse Events (MAEs) at 30 days.

The MAE endpoint and its components will be summarized by counts and percentage for the AT cohort. Data Monitoring Committee (DMC) adjudicated data will be used in the analysis.

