#### **4. ANALYSIS POPULATIONS**

This clinical study will enroll 60 patients. This sample size was established based on typical sample sizes for early feasibility studies and no statistical justification was utilized.

It was decided that from an analysis perspective, data from the first 30 patients (patient enrolled before Rev L) and second 30 patients (Patient enrolled under Rev L and after) will be analyzed together and also separately by sub-groups of before rev L and rev L and after, where applicable.

The analysis population will be grouped into three analysis cohorts that in total comprise all the patients in whom the study procedure has been attempted (vascular access obtained) in this study. The analysis cohorts are defined below:

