##### **4.1 Intent-to-Treat (ITT) Population**

The Intention-to-Treat (ITT) population includes all patients who signed informed consent, met eligibility criteria, and in whom the study procedure has been attempted (i.e. at least skin incision to introduce the FORMA System).

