##### **4.2 As-Treated (AT) Population**

The As-Treated population (AT) is a subset of the ITT population and includes all patients in whom the study device is implanted and remains in position at the time of the patient's exit from the procedure room.

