##### **4.3 Per-protocol Population**

The Per-Protocol (PP) population is a subset of the As-Treated (implanted) population in whom there are no inclusion/exclusion criteria-related protocol deviations.

The AT population will be the primary analysis population for performance and safety assessment. The ITT population will be used for device success, and additional safety analyses. Additional analyses of performance and safety data using the PP population will also be performed, if there is a clinically meaningful difference in sample size from the as-treated population.

 Edwards	Revision Date: April 1, 2019		Rev	3.0	For Use Only by Affiliates of Edwards Lifesciences	Page 13 of 18
	Title	Statistical Analysis Plan for FORMA EFS				

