### 8.2 Performance Endpoints

All performance endpoints will be summarized by counts and percentages.

Device success is based on procedure data only. It will be evaluated for the ITT and AT cohorts at the time of the patient's exit from the cardiac catheterization laboratory.

The procedure success endpoint will be assessed for the AT cohort. The endpoint and its components will be assessed at the index procedure hospital discharge.

The clinical success endpoint at 30 days will be summarized by counts and percentages for the AT cohort. DMC adjudicated data will be used for MAEs. The endpoint and its components will be assessed at the 1 month follow-up interval.

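### The adjudicated 30-day MAE composite, procedural success and clinical success are specified for the as-treated cohort only, so attempted patients who leave the room without the device in position are outside all three rates

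*SAP*

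**What the plan says.** SAP 4.3 sets the general rule: "The AT population will be the primary analysis population for performance and safety assessment". Protocol 13.2 says the same. The endpoint sections follow it:

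- **MAE (SAP 8.1):** "The MAE endpoint and its components will be summarized by counts and percentage for the AT cohort". Committee-adjudicated data are to be used.
- **Procedural success (SAP 8.2; Protocol 13.4 agrees):** "The procedure success endpoint will be assessed for the AT cohort".
- **Clinical success (SAP 8.2; Protocol 13.5 agrees):** "The clinical success endpoint at 30 days will be summarized by counts and percentages for the AT cohort".

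SAP 4.2 limits AT to ITT patients "in whom the study device is implanted and remains in position at the time of the" exit from the procedure room. SAP 4.1 defines ITT as patients who "signed informed consent, met eligibility criteria, and in whom the study procedure has been attempted", with skin incision as the minimum. Protocol 8.2 counts a patient as enrolled at that same skin incision.

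ITT has two stated uses: device success, and additional safety analyses. SAP 8.4.3, which carries the second title, specifies site-reported AEs and SAEs split at 30 days, plus a listing. It does not mention the adjudicated MAE composite.

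**The concern.** Membership of AT is decided by something that happens after the patient has been exposed to the procedure. A patient with a failed attempt has had the access, the anaesthesia and the catheter work, and counts towards the 60, but contributes to none of these three rates.

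The study's objectives are the safety and function of the system and guidance for later designs. A planner of the next study needs to know what happens when the procedure is started. The AT rates answer a narrower question: what happens once the device is in place at the end of the procedure.

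The plan also reports patients enrolled before Rev L and from Rev L onward separately (SAP 4 and 8.4.4). If the two halves have different numbers of failed attempts, their AT success rates move by different amounts, and the half with more failures gains more.

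**Working it through.** **Inputs from the documents.** Planned enrolment is N = 60 (Protocol 13.1, SAP 2.3), with two groups of 30 around Rev L (SAP 4). Both documents say the 60 has no statistical justification, so there is no power or precision figure to reproduce. The documents give no number of failed attempts, success rate or MAE rate. All such values below are assumptions.

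**Step 1: can a non-AT patient be a success?** SAP 3.2.1 judges deployment as intended at exit from the catheterization laboratory. If that requires the device in position at exit, a non-AT patient fails device success. Procedural success requires device success (SAP 3.2.2), and clinical success requires procedural success (SAP 3.2.3). The patient therefore fails all three.

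**Step 2: the success rates.** Let s be the number of successes, the same in both cohorts, and f the number of attempted patients outside AT. With complete data:

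AT rate ÷ all-attempted rate = [s/(N−f)] ÷ [s/N] = N/(N−f)

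In general N is N(ITT). With N = 60:

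| f (assumed) | Factor | Example (s assumed) |
|---|---|---|
| 0 | 60/60 = 1.000 | no change |
| 1 | 60/59 = 1.017 | 40/59 = 67.8% vs 40/60 = 66.7% |
| 3 | 60/57 = 1.053 | 40/57 = 70.2% vs 40/60 = 66.7% |
| 6 | 60/54 = 1.111 | 38/54 = 70.4% vs 38/60 = 63.3% |

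The gap in percentage points is (AT rate) × f/60. For AT success between 50% and 80% it is 0.8 to 1.3 points at f = 1, 2.5 to 4.0 at f = 3 and 5.0 to 8.0 at f = 6. For scale, the Clopper-Pearson 95% interval for 38/54 is 56.4% to 82.0%, and for 38/60 it is 49.9% to 75.4%. Each is about 25 points wide.

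**Step 3: the Rev L subgroups.** With 30 per group the factor is 30/(30−f), or 30/27 = 1.111 at f = 3. Suppose 20 of 30 attempted patients succeed in each half, with f = 3 in one half and f = 0 in the other. AT then shows 20/27 = 74.1% against 20/30 = 66.7%, a 7.4-point difference produced by the denominator alone.

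**Step 4: MAE.** Let x AT patients and y of the f others have an MAE. AT gives x/(N−f), and all attempted gives (x+y)/N. AT understates the all-attempted rate only if y/f exceeds x/(N−f). With x = 8 and f = 6 (assumed), AT is 8/54 = 14.8%:

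| y of 6 | All attempted |
|---|---|
| 0 | 8/60 = 13.3% |
| 1 | 9/60 = 15.0% |
| 2 | 10/60 = 16.7% |
| 3 | 11/60 = 18.3% |

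The sign is not fixed.

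**Step 5: what could be rebuilt from the specified output.** ITT and AT counts are reported (SAP 7.1), so all-attempted success is largely recoverable as s/N(ITT). The adjudicated MAE rate is not, because y is specified only through site-reported events.

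**The case against.** The strongest reply is that AT is defined openly and used consistently, and that failed attempts are not hidden. Device success is given for ITT and AT, implantation status is summarised (SAP 7.4), and ITT AEs and SAEs are tabulated to 30 days with a full listing. All of that stands. A reader might infer that failures are concealed, and the documents do not support that. What is left is that none of this output is the adjudicated composite.

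Four further inferences are tempting and also go too far:

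- **That the success rates are known to be inflated.** The number of failed attempts is not in the documents and may be 0. The factor also needs complete data and the reading of device success in Step 1. The literal wording does not expressly bar a patient whose device was deployed and then lost position before exit.
- **That AT understates MAE risk.** Step 4 shows it can go either way.
- **That adding ITT would achieve nothing, because SAP 6.1 removes patients with missing data and a failed implant may lack a discharge EROA.** Applied mechanically at f = 6, that would give 38/57 = 66.7% with three values missing and 38/54 = 70.4% with all six missing. But SAP 6.1 states a general convention that allows exceptions, and a device failure already settles the outcome without EROA. This is a possible misreading that one sentence can prevent.
- **That ITT must be smaller than the attempted group because its definition mentions eligibility.** The per-protocol cohort is the AT subset "in whom there are no inclusion/exclusion criteria-related protocol deviations", which implies that patients with such deviations can be in AT and hence in ITT. ITT plausibly equals all enrolled patients, though it would help to say so.

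The table shells and one redacted item in SAP 6.1 cannot be seen, so the point is confined to the visible text. The objection that the shifts are small against the intervals is also fair. It bears on priority and does not remove the gap.

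**Conclusion.** The point holds in this form. As written, the plan gives the adjudicated 30-day MAE composite, procedural success and clinical success for AT only, and no section specifies adjudicated MAE for all attempted patients.

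Given complete data and the Step 1 reading of device success, AT success exceeds all-attempted success by N(ITT)/(N(ITT)−f). That is nothing at f = 0, under 2% in relative terms at f = 1, and 11% at f = 6 of 60 or f = 3 of 30. No factor or direction can be stated for MAE.

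This is a cheap improvement. The study has no hypothesis or success threshold, so interpretation of the rates is affected, including the comparison of the Rev L subgroups, and no formal decision changes.

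**What to change.** In SAP 4.3, 8.1 and 8.2 and Protocol 13.2, 13.4 and 13.5:

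1. Report the adjudicated 30-day MAE composite and its components, procedural success and clinical success for ITT beside AT, overall and in the two Rev L subgroups. State that ITT here means all patients with skin incision.
2. State that a patient without the device in position at room exit counts as a procedural and clinical failure, whether or not a discharge EROA exists.
3. Reconcile Protocol 8.7.1, which schedules post-procedure visits for implanted patients, with Protocol 8.10, which keeps attempted but non-implanted patients until the 1-month visit, so that 30-day MAE status is collected for everyone attempted.

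The cost is wording, one extra table column, and adjudication of the few events in non-implanted patients. Little new data is needed, because Protocol 8.10 already keeps these patients to 1 month. The downside for the sponsor is that reported success may be slightly lower.
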